### 8.3.4 Removal of Subjects from Therapy or Assessments

Subjects may stop study medication for any of the following reasons:

- Subject request.
- Use of nonpermitted concurrent therapy.
- Noncompliance with the study medication (see Section 8.5.9).
- Noncompliance with the study procedures (see Section 8.5.9 and Section 8.6).
- Lost to follow-up.
- Occurrence of AEs not compatible with the continuation of subject participation in the study, in the investigator's opinion. This also includes any clinically significant laboratory results, ECGs, and vital signs.
- Investigator request.
- Sponsor request.
- Treatment failure deemed by the investigator as lack of improvement or worsening of the disease symptoms or occurrence of intolerable AEs.

Treatment with GLPG0634 will be discontinued and the patient withdrawn from this study for:

- Serious infections (those requiring parenteral antimicrobial therapy or hospitalization).
- Any opportunistic infections.
- Complicated herpes zoster infection (multi-dermatomal, disseminated, ophthalmic or CNS involvement).
- Two sequential total white cell counts  $<2000$  cells/mm^3 (SI:  $<2.0 \times 10^9$  cells/L).
- Two sequential neutrophil counts  $<1000$  neutrophils/mm^3 (SI:  $<1.0 \times 10^9$  cells/L).
- Two sequential lymphocyte counts  $<750$  lymphocytes/mm^3 (SI:  $<0.75 \times 10^9$  cells/L).
- Two sequential hemoglobin  $<8.0$  g/dL (SI:  $<80$  g/L).
- Two sequential platelet counts  $<75,000$  platelets/mm^3 (SI:  $<75.0 \times 10^9$  cells/L).
- Two sequential AST or ALT elevations  $>3$  times the upper limit of normal with at least one total Bilirubin value  $>2$  times the upper limit of normal.
- Two sequential AST or ALT elevations  $>3$  times the upper limit of normal accompanied by symptoms consistent with hepatic injury.
- Two sequential AST or ALT elevations  $>3$  times the upper limit of normal accompanied by elevated INR.
- Two sequential AST or ALT elevations  $>5$  times the upper limit of normal, regardless of total Bilirubin or accompanying symptoms.
- Two sequential increases in serum creatinine  $>50\%$  over the average of screening and baseline values.
- Two sequential decreases from the baseline of inhibin B by 50% or Testosterone by 50% with concurrent increases in FSH or LH respectively.

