3.2. ANALYSIS PERIODS FOR NON-VISIT DATA

These analysis periods are to be used for allocation of adverse events and concomitant medications into periods.

Analysis period	Period start date	Period end date
Screening	Date of signing the initial ICF.	First study drug administration date – 1 day.
First 12 weeks	First study drug administration date.	Date of the W12 visit.
Second 12 weeks	Date of the W12 visit + 1 day.	Max (trial termination date ; date of last dose + 30 days).
Full 24 weeks	First study drug administration date.	Max (trial termination date ; date of last dose + 30 days).

The trial termination date is the date of last contact with the subject, as recorded in the eCRF.

Note that the last analysis period in case of early termination will always be ended by: *Maximum (trial termination date ; date of last dose + 30 days)*. In case the subject rolls over to DARWIN3, the trial termination date will be used (no 30 days will be added since that would be during DARWIN3).

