4.4.2. Handling of missing values in scales or summary parameters

Missing items in scales or summary parameters will be imputed to allow for the derivation of the total scale/parameter score. The appropriate imputation rules will be described in the sections where the total scores are defined.

4.4.3. Handling of missing values and early dropouts in the efficacy analyses during the first study period (up to Week 12)

This is for the “efficacy chapter 2” analysis.

For binary data (e.g., ACR20), two different imputations will be done for missing visits as well as early dropouts: non-responder imputation (NRI) and LOCF, up to and including Week 12. The NRI imputation will be primary, and LOCF will be secondary.

For other data (ordinal or continuous), missing visits as well as early dropouts will be imputed using the last observation carried forward (LOCF) algorithm, up to and including Week 12.

Definitions of the imputation methods:

- LOCF (all types of parameters, from binary to continuous): to impute a missing value, the last preceding nonmissing value will be used (which could even be a baseline value).
- NRI (binary response parameters only): to impute a missing response, the subject will be assumed to be a non-responder.

For all parameters, an observed-case analysis will also be performed (i.e., without any imputation). The observed-case analysis will serve as a sensitivity analysis (to ascertain the impact of early dropouts on the results) and will basically be limited to:

- ACR20/50/70/N: descriptive at W12+W24 and inferential at W12
- EULAR remission: descriptive at W12+W24
- SDAI/CDAI: descriptive at BSL+W12+W24
- DAS28: descriptive at BSL+W12+W24 and inferential at W12
- All ACR components (VAS, joint counts, CRP, HAQ-DI): descriptive at BSL+W12+W24
- QoL (FACIT,SF-36): descriptive at BSL+W12+W24.

4.4.4. Handling of missing values and early dropouts in the efficacy analyses during the study period as a whole (full 24 weeks)

This is for the “efficacy chapter 2” analysis.

For binary data (e.g., ACR20), two different imputations will be done for missing visits as well as early dropouts: non-responder imputation (NRI) and LOCF, up to and including Week 24. The NRI imputation will be primary, and LOCF will be secondary.

For other data (ordinal or continuous), missing visits as well as early dropouts will be imputed using the last observation carried forward (LOCF) algorithm, up to and including Week 24.

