8.1. ACR20, ACR50, ACR70 AND ACR-N**8.1.1. Parameters**

ACR20 response when:

- $\geq 20\%$ improvement from baseline in SJC66, and
- $\geq 20\%$ improvement from baseline in TJC68, and
- $\geq 20\%$ improvement from baseline in at least 3 of the following 5 items:
 - Pain VAS (taken from the HAQ-DI)
 - Patient's Global Assessment of Disease Activity VAS
 - Physician's Global Assessment of Disease Activity VAS
 - Total HAQ-DI score
 - CRP.

Subjects who do not meet this criterion are non-responders.

If any of the 7 components of the ACR20 would be missing, then this missing component will be imputed using the value of the last preceding nonmissing visit. If all components are missing, then the derived ACR20 will remain missing. Imputation of such cases for the tables will be done there using LOCF or NRI like any other missing value.

Subjects who discontinue within the first week so that ACR20/50/70 responses cannot be determined will be classified as non-responders.

The ACR50 and ACR70 responses are derived using the same algorithm, but with 50% and 70% cutoffs respectively.

Note that the primary endpoint of the study is the ACR20 at Week 12 in the ITT population, using NRI imputation.

The ACR-N is derived using the following formula:

ACR-N = MIN [% improvement in TJC68, % improvement in SJC66, MED % improvement in (patient's global assessment, physician's global assessment, patient's assessment of pain, HAQ-DI, CRP)]

So this is taking the smallest of the percentage increases in SJC66, TJC68, and the third of the remaining 5 parameters. In case the ACR-N is negative (i.e., the subject actually worsens instead of improves), then the ACR-N is replaced by a 0. The ACR-N is therefore a number between 0 and 100.

The ACR-N represents the percentage NN% according to which the subjects would have been an "ACRNN" responder.

(See further sections on how to derive these components.)

The time to ACR20 response

= (date of first time ACR20 response is reached) – (date of first medication intake) + 1 day, if the subject achieved ACR20 response during the initial 12 weeks treatment period, or
= MIN (date of the Week 12 visit, date of trial termination) – (date of first medication intake) + 1 day, in case the subject did not achieve ACR20 response at any time during the initial 12 weeks treatment period.

Next to this, the visit during which the ACR20 response was first recorded will be analyzed as well:

- Week 1
- Week 2
- Week 4
- Week 8
- Week 12

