- Never (i.e., subject did not achieve ACR20 response during the initial 12 weeks of treatment).

The time to ACR50 response and the time to ACR70 response are defined in the same way.

Note that the study period 2 cannot be used for the time-to-event derivation, because of the predefined potential treatment shifts at Week 12.

Note that if for a specific visit both the regular CRP as well as the high-sensitive CRP are available, the high-sensitive CRP will be used for the derivation of the percentage change from baseline and also for the ACR20/50/70/N.

Note that the percentage change from baseline remains missing if the baseline value itself equals zero.

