Frequency per time point (weeks 12 and 24 only), and per treatment group. ACR-N will be presented in the following categories:

<10,
[10,20[,
[20,30[,
[30,40[,
[40,50[,
[50,60[,
[60,70[,
[70,80[,
[80,90[,
[90,100].

The “raw” SAS PROC output must be provided in a statistical appendix listing.

The table will show:

- LOCF in ITT
- observed-case in ITT (descriptive at week 12 + 24; inferential statistics at Week 12 only).

Table to be created for the Week 12 interim analysis as well, cut off at Week 12.

Table 14.2.1.1.10: ACR-N: Exploratory pairwise comparisons among the dose groups

ANOVA model at each time point. Factors in the model are: treatment, region, and previous use of biologics.

Per time point, the table will present:

- Per group: difference in LS-means versus the other GLPG0634 groups, together with a 95% confidence interval of this difference.
- Per group: p-value for pairwise comparison versus the other GLPG0634 groups. These p-values will be presented both as uncorrected p-values, and are derived as contrasts within the overall model. As this is a purely exploratory analysis, no adjustment for multiplicity will be performed.

The “raw” SAS PROC output must be provided in a statistical appendix listing.

The table will show:

- LOCF in ITT
- observed-case in ITT (inferential statistics at Week 12 only).

Table to be created for the Week 12 interim analysis as well, cut off at Week 12.

Table 14.2.1.1.11: Time to ACR20 response: Descriptive statistics and between-group comparison

Descriptive statistics per treatment group.

Between-group comparison (overall and all pairwise comparisons versus placebo)

P-values are generated from a Cox proportional hazards regression model. Factors in the model are: treatment, region, and previous use of biologics.

The table will present:

- Per group: N (number of events, number of censored, number in total), mean (SE), median, quartiles.
- Overall type-III p-values for treatment, region and previous use of biologics.
- Per group: p-value for pairwise comparison versus the placebo group. These p-values will be corrected for multiplicity according to Hommel's closed-testing method as implemented in SAS PROC MULTTEST. The uncorrected p-values will also be presented.

A frequency table of the time-to-event in categories (Week 1, Week 2, Week 4, Week 8, Week 12, never) will also be presented.

The "raw" SAS PROC output must be provided in a statistical appendix listing.

Population: ITT.

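### Time to ACR20/50/70 response censors non-responders at withdrawal or at their own Week 12 visit date, so the Kaplan-Meier response overstates the proportion who ever responded and the Cox p-values can shift either way

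*SAP*

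**What the plan says.** SAP 8.1.1 measures time to ACR20 response from first intake to the first visit with a response during the initial 12 weeks. A subject without one is followed to "MIN (date of the Week 12 visit, date of trial termination"). On ACR50 and ACR70 it says: "The time to ACR50 response and the time to ACR70 response are defined in the same way". SAP 3.2 fixes the second date: "The trial termination date is the date of last contact with the subject, as recorded in the eCRF".

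Table 14.2.1.1.11 (SAP 8.1.2) reports, per group, "N (number of events, number of censored, number in total), mean (SE), median, quartiles". It then states: "P-values are generated from a Cox proportional hazards regression model". The comparisons with placebo are Hommel-adjusted, and Kaplan-Meier plots follow in SAP 8.1.3. The same table also tabulates the visit of first response, with a last row defined as "Never (i.e., subject did not achieve ACR20 response during the initial 12 weeks of treatment".

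Among the reasons for stopping study medication, Protocol 8.3.4 lists "Treatment failure deemed by the investigator as lack of improvement or worsening of the disease symptoms or occurrence of intolerable AEs". For binary responses with missing visits or early dropout, SAP 4.4.3 says: "The NRI imputation will be primary, and LOCF will be secondary".

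**The concern.** Kaplan-Meier and Cox methods assume that a censored subject keeps the same chance of responding as those still followed at that time. A subject who leaves because the drug is not working does not fit that assumption. The plan neither justifies the assumption nor provides a sensitivity analysis for time to response.

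Two features of the dates add to this.
- Trial termination is last contact. For an early discontinuer that can be the follow-up visit 7 to 10 days after the early discontinuation visit, where no efficacy is assessed (Protocol 8.6.3). Time in which a response cannot be seen then counts as time at risk.
- Completers without response are censored at their actual Week 12 visit date. A responder seen late in the visit window is compared with a risk set that has already lost the non-responders seen a day or two earlier.

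At stake are the printed curve, its median and quartiles, and the adjusted p-values of a secondary analysis in a dose-finding study.

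**Working it through.** **The plan's own figure.** None is stated for time to response. The only computed design figure is the power for ACR20 at Week 12 (Protocol 8.8.2). With 70 per arm and two-sided alpha 0.05/3 (the protocol does not state sidedness), it reproduces:
- 15% vs 43%: 90.7%, and 40% vs 70%: 89.1% (stated 90%)
- 15% vs 39%: 79.8%, and 40% vs 67%: 80.0% (stated 80%)

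These supply the arm size and response rates used in step 3. Dropout rates and timing are assumptions throughout.

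**1. Withdrawal of non-responders.** Take 70 subjects of whom 21 (30%) respond, first at Weeks 1, 2, 4, 8 and 12 in numbers 3, 4, 5, 5 and 4 (assumed). The Kaplan-Meier response is 1 − Π(1 − d/n), where d is the number of first responses at a visit and n the number still at risk.
- No dropout, n = 70, 67, 63, 58, 53: 1 − 49/70 = 30.0%.
- 7 non-responders leave (10%; 2, 3 and 2 after Weeks 2, 4 and 8), n = 70, 67, 61, 53, 46: 1 − (63/70)(56/61)(48/53)(42/46) = 31.7%.
- 11 leave (16%; 3, 4, 4), n = 70, 67, 60, 51, 42: 1 − (63/70)(55/60)(46/51)(38/42) = 32.7%.
- 14 leave (20%; 4, 5, 5), n = 70, 67, 59, 49, 39: 1 − (63/70)(54/59)(44/49)(35/39) = 33.6%.

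In every case 21/70 = 30% ever responded and 'Never' is 70%. A simulation with responses spread over Weeks 1 to 12 gave 31.9%, 33.0% and 34.3% at 10%, 15% and 20% dropout.

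**2. Scattered Week 12 dates, no dropout.** Protocol 8.6.2.5 allows Day 85 ± 2, and the SAP 3.3 window is Days 71 to 98. In the same example 53 subjects reach Week 12. Let the four responders be seen on Days 83, 84, 86 and 87, and the 49 non-responders on Days 83 to 87 in numbers 10, 10, 9, 10 and 10. At the four responses n = 53, 42, 22 and 11:

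1 − (53/70)(52/53)(41/42)(21/22)(10/11) = 37.1%, although 30% responded.

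Averages over 4,000 simulated arms of 70 (true 30%, first responses equally likely at each visit, visit days uniform within ±2):

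| Rule for subjects without response | No dropout | 15% dropout |
|---|---|---|
| SAP 8.1.1 | 36.8% | 41.0% |
| Discontinuers at Day 85, completers at actual visit | 36.8% | 38.5% |
| All at one common time (Day 98) | 30.0% | 30.0% |

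**3. The Cox comparison.** Expected counts, 70 per arm, responses on the target days; the hazard ratio is unadjusted. 'Reference' keeps non-responding withdrawals at risk to Week 12.

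| Withdrawn without response, placebo/active | 15% vs 43%: HR (z) | 40% vs 70%: HR (z) |
|---|---|---|
| Reference | 3.29 (3.32) | 2.11 (3.14) |
| 10%/3% | 3.20 (3.25) | 2.05 (3.01) |
| 20%/5% | 3.09 (3.15) | 1.96 (2.83) |
| 30%/5% | 2.94 (3.01) | 1.83 (2.54) |
| 10%/10% | 3.33 (3.35) | 2.17 (3.25) |
| 5%/15% | 3.52 (3.50) | 2.34 (3.55) |

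The sign of the shift changes with the balance of withdrawals. With earlier withdrawals at 30%/5%, the hazard ratio falls to 2.71 and 1.66. The placebo curve in the 40% case then reads 52.6%, so a median time to response would be printed for an arm in which 40% ever responded.

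**The case against.** Censoring at withdrawal is a conventional, prespecified choice for a secondary analysis in an exploratory study. The early discontinuation visit includes a full efficacy assessment, so a subject who attends it is assessed before being censored. The uncensored proportion is already in the same table through the 'Never' row, and response by visit with non-responder imputation is tabulated separately. Every withdrawal modelled above is a subject who would never have responded, which is near the worst case. The dropout shifts are also small against sampling error: √(0.3 × 0.7/70) = 5.5 points at 30%. For the 20%/5% case the log hazard ratio moves by ln(2.11/1.96) = 0.07, against a standard error of about √(1/28 + 1/49) = 0.24. All of this stands and limits the weight of the point. It does not remove the upward bias of the curve.

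Stronger readings that the documents do not support:
- *The plan contradicts itself.* The primary endpoint is response at Week 12; this parameter is first response at any visit up to Week 12. A subject who responds at Week 4 and loses the response counts differently in each, with no dropout at all. 'Never' describes what was observed and is compatible with censoring.
- *The comparisons are pulled toward no effect.* That needs more non-responders lost on placebo. Protocol 8.3.4 also lists infection, laboratory and hormone criteria and adverse events, and nothing says which arm will lose more.
- *The reported hazard ratios are biased.* The table specifies p-values; hazard ratios would appear only in the appended SAS output.
- *Censoring is informative by design.* Treatment failure is one of many permitted reasons, and the quoted item also covers intolerable adverse events. The rule that permanent stopping means leaving the study appears only as an action-taken category for adverse events. The supportable wording is that censoring can be informative.

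It may also seem inconsistent to fault a few unassessed days and then propose following discontinuers to Week 12. The proposal openly applies a non-responder policy. It is the analysis that relies on non-informative censoring that should stop the clock at the last efficacy assessment.

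**Conclusion.** The point holds as a minor one. The Kaplan-Meier response at Week 12 exceeds the proportion who ever responded whenever non-responders withdraw, by about 2 to 4 points on a true 30% at an assumed 10% to 20% dropout. Scatter in the Week 12 visit dates inflates the end of the curve by about 7 points in the ±2-day example even without dropout, and is the larger of the two effects. The Cox p-values are distorted in a direction that depends on which arm loses more non-responders; the effect of visit scatter on them was not computed.

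The sizes rest on assumed dropout rates, timing of response and withdrawal, and visit spread, none of which the documents give. If few subjects leave before Week 12, only the visit-date effect remains. A reader might infer that the primary result is at risk; it is not, because ACR20 at Week 12 with non-responder imputation does not use these times.

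**What to change.** In SAP 8.1.1, replace the second branch of the definition. Every subject without a response by Week 12, completer or early discontinuer, is censored at one common time at or after the last possible Week 12 assessment, for example Day 98, the upper bound of the Week 12 window in SAP 3.3. Analysis by nominal visit, with non-responders censored after the Week 12 responses, serves equally well. Apply it to ACR20, ACR50 and ACR70. The end of the curve then equals one minus 'Never'. Moving only the discontinuers to Day 85 is not enough, as the second row of the table in step 2 shows.

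Keep censoring at the last efficacy assessment, not at last contact, as a sensitivity analysis.

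Cost: one line in the derivation, one extra sensitivity run, and slightly lower Kaplan-Meier response rates. No new data are needed. The SAP does not mark the time-to-response tables for the Week 12 interim analysis, so no interim output changes.

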3.3. ALGORITHM OF ALLOCATING VISITS TO TIME WINDOWS

All visits (including early discontinuation visits and unscheduled visits but excluding visits without data) will be placed into time windows according to their relative day (DY) in the study, according to the following allocation table:

Time point label	Target day	Interval lower bound	Interval upper bound
Screening (3)	NA	NA	NA
Baseline (1)	NA	NA	NA
Week 1	8	2	11
Week 2	15	12	21
Week 4	29	22	42
Week 8	57	43	70
Week 12	85	71	98
Week 16	113	99	126
Week 20	141	127	154
Week 24	169	155	182
>Week 24 (2)	NA	183	+∞
Follow-up (3)	7-10 days after last visit	NA	NA

(NA = not applicable).

Notes:

- (1) The actual baseline reference value will be determined per parameter as the last available pre-dosing data point, so might differ from this “baseline” visit interval. There will be only one baseline time point in this study: the last nonmissing value prior to first dosing of study drug.
- (2) Visits falling really late in the study (relative day > 182; excluding the follow-up visit) will be allocated to a “>Week 24” interval, and will not be shown in tables nor figures, but will only be listed.
- (3) For the screening and follow-up visits, no time window is defined. The visit as recorded in the eCRF will be used. Follow-up visits of subjects who discontinue the study prior to the Week 12 re-randomization will be shown separately as well in the tables that present the first part of the study only. For tables that present the study as a whole, all follow-up visits will be shown.

Tables, figures and listings will present the time points, not the visits.

For ECGs, a different method will be used. See section 12.3 for the details.

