8.3. SDAI AND CDAI SCORES

8.3.1. Parameters

SDAI = TJC28 + SJC28 + patient's disease activity VAS (in cm)+ investigator's disease activity VAS (in cm) + CRP (in mg/dL).

CDAI = TJC28 + SJC28 + patient's disease activity VAS (in cm)+ investigator's disease activity VAS (in cm).

(TJC28 and SJC28 are the 28 joint counts for tenderness and swelling. See further sections on how to derive these components.)

CDAI and SDAI scores can only be derived when all components are nonmissing. If any of the components would be missing, then this missing component will be imputed using the value of the last preceding nonmissing visit.

Note that if for a specific visit both the regular CRP as well as the high-sensitive CRP are available, the high-sensitive CRP will be used for the derivation of the SDAI.

Apart from the actual scores, the changes from baseline and percent changes from baseline will be derived.

The SDAI is also categorized:

- High disease activity: SDAI > 26
- Moderate disease activity: SDAI in] 11 , 26]
- Low disease activity: SDAI in] 3.3 , 11]
- Remission: SDAI ≤ 3.3

The CDAI is also categorized:

- High disease activity: CDAI > 22
- Moderate disease activity: CDAI in] 10 , 22]
- Mild disease activity: CDAI in] 2.8 , 10]
- Remission: CDAI ≤ 2.8

Note that the percentage change from baseline remains missing if the baseline value itself equals zero.

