8.4. DAS28(CRP)

8.4.1. Parameters

$$\text{DAS28(CRP)} = 0.56 \times \sqrt{\text{TJC28}} + 0.28 \times \sqrt{\text{SJC28}} + 0.36 \times \text{Ln}[1 + \text{CRP (in mg/L)}] + 0.014 \times \text{patient's disease activity VAS (in mm)} + 0.96$$

(TJC28 and SJC28 are the 28 joint counts for tenderness and swelling. See further sections on how to derive these components. Ln = natural logarithm.)

DAS28(CRP) scores can only be derived when all components are nonmissing. If any of the components of the DAS28(CRP) would be missing, then this missing component will be imputed using the value of the last preceding nonmissing visit.

Note that if for a specific visit both the regular CRP as well as the high-sensitive CRP are available, the high-sensitive CRP will be used for the derivation of the DAS28(CRP).

Note that the percentage change from baseline remains missing if the baseline value itself equals zero.

Next to the actual DAS28(CRP) value, also the changes and percent changes from baseline will be derived.

Categorization of the DAS28(CRP) scores:

- High disease activity: > 5.1
- Moderate disease activity:] 3.2 , 5.1]
- Low disease activity: [2.6 , 3.2]
- Remission: < 2.6

A second categorization of the DAS28(CRP) into EULAR response categories (none, moderate, good) will be done according to the following:

Actual DAS28(CRP)	Improvement in DAS28(CRP) from baseline:		
	> 1.2] 0.6, 1.2]	≤ 0.6
≤ 3.2	Good	Moderate	None
] 3.2, 5.1]	Moderate	Moderate	None
> 5.1	Moderate	None	None

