8.8. ACR COMPONENT: SERUM CRP

8.8.1. Parameters

Serum CRP (mg/L) will be analyzed as raw values, change from baseline and percent change from baseline.

Note that if for a specific visit both the regular CRP as well as the high-sensitive CRP are available, the high-sensitive CRP will be used in the analysis tables and figures. The regular CRP will then only be listed.

CRP and hsCRP values will also be categorized according to the lab's normal ranges: normal (value \leq ULN) or high (value $>$ ULN), where ULN = upper limit of the normal range as provided by the central lab. Note that the same ULN (8.999) will be applied to both CRP and hsCRP.

Note that CRP and hsCRP will be excluded from the lab safety analysis.

Note that the percentage change from baseline remains missing if the baseline value itself equals zero.

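### The CRP assay is chosen visit by visit, so a CRP change can compare two assays even when a same-assay pair exists

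*SAP*

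**What the plan says.** SAP section 8.1.1 fixes the assay one visit at a time: "if for a specific visit both the regular CRP as well as the high-sensitive CRP are available, the high-sensitive CRP will be used". The value so chosen feeds CRP percent change and all four ACR measures (20, 50, 70 and N). Section 8.8.1 applies the same choice to the CRP tables and figures and adds "The regular CRP will then only be listed". Sections 8.3.1 and 8.4.1 repeat it for SDAI ("the high-sensitive CRP will be used for the derivation of the SDAI") and for DAS28(CRP).

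Three other rules bear on which CRP value is used, and none mentions the assay:

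- Baseline (SAP 3.3, note 1): "There will be only one baseline time point in this study: the last nonmissing value prior to first dosing of study drug".
- A missing ACR component (SAP 8.1.1): "this missing component will be imputed using the value of the last preceding nonmissing visit".
- Normal/high classification (SAP 8.8.1): "Note that the same ULN (8.999) will be applied to both CRP and hsCRP".

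The protocol's visit descriptions (section 8.6) and flow chart (8.7.1.5) schedule serum CRP and do not name a high-sensitivity test. Listing 16.2.6.8 in the SAP shows CRP and hsCRP values, so the SAP expects both in the database. Neither document says at which visits or for which subjects hsCRP was run.

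**The concern.** A percent change means what it says only if both values are on the same scale. The conditional wording of the rule anticipates visits where only one assay is available. Suppose a subject has only regular CRP at baseline and both assays at Week 12. The rule then picks regular CRP for one end of the comparison and hsCRP for the other, and sends the matching regular Week 12 result to the listing. Any systematic difference between the assays is then counted as improvement or worsening.

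This is a defect in a stated rule rather than a missing detail, because the rule discards a usable same-assay pair. CRP is one of the five items of which three must improve by at least 20% for ACR20, the primary endpoint at Week 12. It also enters ACR50, ACR70, ACR-N and the CRP change tables.

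**Working it through.** **Figures in the plan.** The plan gives no figure for assay agreement or for how often assays differ between visits, so there is none to reproduce on this point. The design power, which this point does not dispute, does reproduce. With 70 per arm, alpha 0.05/3 and a two-sided chi-square test, power is 90.7% for 43% v 15% and 89.1% for 70% v 40% (stated 90%), and 79.8% for 39% v 15% and 80.0% for 67% v 40% (stated 80%).

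**Step 1: apply the rule to each availability pattern.** Each cell shows the assay used at baseline, then at Week 12.

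| Available at baseline | Week 12: regular only | Week 12: hsCRP only | Week 12: both |
|---|---|---|---|
| Regular only | regular, regular | **regular, hs** (no common assay) | **regular, hs** (regular exists at both) |
| hsCRP only | **hs, regular** (no common assay) | hs, hs | hs, hs |
| Both | **hs, regular** (regular exists at both) | hs, hs | hs, hs |

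Four of the nine patterns mix assays. In two of these four, the rule passes over a regular-CRP pair that could have been used. In the other two no common assay exists, so no choice of rule can avoid the mixing.

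**Step 2: shift in the CRP threshold.** Let k be the hsCRP/regular ratio on the same sample (assumed; not in the documents) and R the true Week 12/baseline ratio.

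- Regular baseline, hsCRP at Week 12: the item is met when k × R ≤ 0.80, so the true fall needed is 1 − 0.80/k.
- hsCRP baseline, regular at Week 12: the item is met when R/k ≤ 0.80, so the true fall needed is 1 − 0.80 × k.

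| Assumed k | Regular, then hs | hs, then regular |
|---|---|---|
| 0.8 | 0% | 36% |
| 0.9 | 11.1% | 28% |
| 1.0 | 20% | 20% |
| 1.1 | 27.3% | 12% |
| 1.2 | 33.3% | 4% |

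The CRP level does not appear in either formula, so a proportional difference acts equally at 6 and at 60 mg/L.

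**Step 3: from the CRP item to ACR20.** By the definition in SAP 8.1.1, the CRP item decides ACR20 only for a subject who meets both joint criteria and exactly two of the other four items. The true fall must also lie between the nominal and the shifted threshold. So

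shift in ACR20 rate = (share with mixed assays) × (share for whom CRP decides) × (share of those flipped).

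All three inputs are assumptions:

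- Low end: 0.05 × 0.05 × 0.10 = 0.00025, about 0.03 percentage points, or 0.02 subjects of 70.
- High end: 0.50 × 0.20 × 0.30 = 0.03, or 3.0 percentage points, or 2.1 subjects of 70.

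The high end multiplies three upper limits and is not a central estimate.

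**Step 4: DAS28(CRP) and SDAI.** Take 0.7 × 8.999 = 6.3 mg/L as an illustrative level, and a 10% difference.

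- DAS28(CRP), CRP term 0.36 × ln(CRP + 1): 10% lower gives 0.36 × ln(7.3/6.67) = 0.032; 10% higher gives 0.36 × ln(7.93/7.3) = 0.030. For a value 10% lower, the shift stays below 0.36 × |ln 0.9| = 0.038 at any CRP level. The EULAR improvement cut-offs are 0.6 and 1.2.
- SDAI, CRP in mg/dL: 0.10 × 0.63 = 0.06. Even at 30 mg/L it is 0.10 × 3.0 = 0.3. The category cut-offs are 3.3, 11 and 26.

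**The case against.** The strongest reply is that no harm has been shown. The protocol schedules one serum CRP test at each efficacy visit, with CRP in the central-laboratory chemistry panel. If hsCRP was run at every visit or at none, assays are never mixed. No document reports a disagreement between the assays, and the 10% is an assumption. The rule is pre-specified and identical in all arms, so unless hsCRP availability depends on response, mixing mainly adds noise. Listing 16.2.6.8 would already let a reader find the affected subjects. All of this stands, and it limits the size of the point. It does not supply a same-assay requirement, and a listing does not correct the tables.

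A reader might infer more than the documents support in four ways:

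- **That the primary result or the power is threatened.** If a loss of 1 or 3 points fell on an active arm alone, power for 43% v 15% would drop from 90.7% to 88.5% or 83.1%. Nothing in the documents suggests such a one-sided loss.
- **That the problem is worse at low CRP, near the entry minimum of 6.3 mg/L.** That minimum is a Screening criterion (protocol 8.3.2, criterion 4). The SAP tabulates baseline CRP below 0.7 × ULN, so it is not a floor for the change. Only an additive or detection-limit difference would matter more at low values, and none can be sized from the documents.
- **That the shared ULN shows the assays disagree, or agree.** It sets one cut-off for both. It is compatible with a common reporting scale and says nothing about agreement within a subject.
- **That DAS28(CRP) and SDAI are materially affected.** Step 4 of the working shows that they are not.

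**Conclusion.** The point holds as a minor flaw in a stated rule. The SAP can compare regular CRP with hsCRP in a change from baseline, and in two of the four mixed patterns it does so although a same-assay pair exists. Under an assumed 10% proportional difference, the CRP item's true threshold moves from 20% to about 11% or 27% (28% or 12% in the reverse order). How many subjects this touches cannot be established from the documents and may be none. The likely effect on Week 12 ACR20 is small: 0.03 to 3.0 percentage points over wholly assumed ranges. The effect is most direct on CRP percent change. It is negligible for DAS28(CRP) and SDAI. The correction is worth making because the rule sits inside the primary endpoint's derivation and costs little to repair.

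**What to change.** In SAP 8.1.1 and 8.8.1, for CRP change, CRP percent change, the ACR20/50/70 CRP item and ACR-N:

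- Use an assay available at both baseline and the visit in question: hsCRP if present at both, otherwise regular CRP if present at both. Take each assay's baseline value from the single baseline time point already defined in 3.3.
- If no common assay exists, keep the measured value under the current rule and flag it. Do not set it to missing: that would trigger the component carry-forward in 8.1.1 and replace a measured Week 12 value with an older one.
- Leave the current rule in 8.3.1 and 8.4.1 for actual SDAI and DAS28(CRP) values, so that the scores and their categories stay defined.

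Flag mixed pairs in Listing 16.2.6.8 and report their number by arm. The Week 12 interim included ACR20 (SAP 6.2), and section 6.3.2 lists no change to the CRP rule since then, so the interim was presumably run under the current rule. Record the change in 6.3.2 and show Week 12 ACR20 under both rules. If there are no mixed pairs, one sentence saying so closes the point.

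The cost is a few sentences and a selection step in the derivation. In some pairs the less sensitive regular assay will be used, and a subject's baseline CRP may come from different assays for different visits. A footnote to the CRP tables should say so.
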